## **9. Evaluation criteria**

### **9.1. Study endpoints**

#### **9.1.1. Primary endpoint**

The primary endpoint will be the evaluation of response rate (CR and PR) of chronic GvHD at 6 months after diagnosis of chronic GvHD and treatment with ATO in combination with prednisone, with or without cyclosporine, as first line treatment.

#### **9.1.2. Secondary endpoints**

The secondary endpoints will be as follows:

- Percentage of patients with documented failure free survival (FFS), defined as death, recurrent or progressive malignancy, or the initiation of a new systemic treatment for chronic GvHD
- Corticosteroids dosage and percentage of reduction in corticosteroids dosage at 6 and 12 months after diagnosis of chronic GvHD and treatment with ATO as first line treatment
- Cumulative incidence of transplant-related mortality (TRM) of infectious and non-infectious origin at 6 and 12 months after diagnosis of chronic GvHD and treatment with ATO as first line treatment
- OS and PFS at 6 and 12 months after diagnosis of chronic GvHD and treatment ATO as first line treatment
- Descriptive analysis of quality of life parameters at inclusion, at 6 and 14 weeks, and at 6, 9 and 12 months after diagnosis of chronic GvHD and treatment with ATO as first line treatment
- Tolerability and safety of ATO in combination with prednisone, with or without cyclosporine, in patients with chronic GvHD after allo-SCT

## **9.2. Assessment of chronic GvHD**

The clinical stage of chronic GvHD will be assessed in each patient at 6 weeks post-inclusion, then again at 14 weeks and 6 months, then a check-up will be performed at 9, and 12 months post-inclusion. The revised grading system proposed by the NIH (see Appendix 1) will be used (Jagasia et al., 2015). Thus the global scoring of chronic GvHD according to the NIH proposal will be performed (Lee et al., 2015). As far as is possible, a single senior physician, (or fellow with advanced and specific training), at each centre will review the organ status of all patients enrolled in this study. Therefore, for documenting chronic GvHD assessment, the investigator will complete the Chronic GvHD Activity Assessment-Clinician Form A (see Appendix 2). In addition, patients will complete the Chronic GvHD Activity Assessment-Patient self-reported Form B, the “Lee Chronic GvHD Symptom Scale” and the FACT-BMT. The Lee symptom scale was developed as a 30-item symptom scale with 7 subscales to capture the chronic GvHD-specific symptom burden. The symptom scale showed to correlate with patients self-assessed mild, moderate, and severe chronic GvHD manifestations in cross-sectional analysis. Longitudinal assessments showed that changes in overall health status correlated best with changes in quality of life as measured by the FACT-BMT. In contrast, changes in chronic GvHD severity were best detected by changes in the Lee symptom scale.

- **The NIH consensus scoring system** for individual organs is used in this study; Organ sites considered include skin, mouth, eyes, GI tract, liver, lungs, joints and fascia, and female genital tract.
  - For skin, the composite score is split into 2 scores to document the extent of skin involvement (BSA) and the specific skin features, separately (see Appendix 6). The higher of the 2 scores is to be used for computation of global severity.
  - For eyes, scoring from 0 to 3 is based on symptoms, need for eye drops, and use of therapeutic procedure or devices.

- For lung, scoring from 0 to 3 is based on symptoms. In addition, pulmonary function tests to assess FEV1 are mandatory in this protocol. For patients with bronchiolitis obliterans, an absolute improvement in FEV1 of 10% predicted or more is considered a PR as long as the initial FEV1 is < 70%. Normalization ( $\geq$  80%) is considered CR.
- For joint and fascia, scoring from 0 to 3 is based on symptoms. The P-ROM score is an exploratory measure that could be very useful in that exploration.
- For mouth, scoring from 0 to 12 is based on symptoms.
- For gastrointestinal tract, scoring from 0 to 3 is performed for the upper and lower gastrointestinal tract and esophagus. In addition patient weight must be recorded.
- For liver, total serum bilirubin, alkaline phosphatase and alanine aminotransferase must be recorded.
- Genital tract requires a specialist exam and measure of genital response are considered exploratory. Therefore, genital tract is not included in evaluation of chronic GvHD response.

Abnormality present but explained entirely by non-chronic GvHD documented cause must be specified and the organ will not be considered as involved for evaluation of chronic GvHD response.

In addition, physician should provide a subjective assessment of current overall chronic GvHD severity on a 4-points scale (no chronic GvHD, mild, moderate or severe) without knowledge of the calculated NIH global severity score. They should also provide an assessment of current overall chronic GvHD severity on a 11-point numerical scale (0 indicates no GvHD manifestation; 10 indicates most severe chronic GvHD symptoms possible). Clinicians should also provide their evaluations of chronic GvHD changes since the last assessment scored on a 7-point scale (very much better, moderately better, a little better, about the same, a little worse, moderately worse, very much worse). These semi-quantitative assessments may detect qualitative improvements that are clinically meaningful but not well captured using other measures.

➤ **Patient reported outcome**

Patient reported outcome included chronic GvHD-specific core measure with the chronic GvHD activity assessment-patient self-report (Lee Symptom Scale: LSS - Form B) and chronic GvHD non-specific ancillary measure with the FACT-BMT. Patients reported outcome are exploratory and will not be used for decision making response evaluation.

- Organ sites considered in the chronic GvHD activity assessment-patient self-report included skin and joint, mouth, genital tract and eyes. In addition, similarly to clinician assessed chronic GvHD, at each assessment, patients should score their perceptions of overall chronic GvHD severity, overall severity of symptoms, and change in symptom severity compared with the last assessment, using the same response options used by clinicians.

- For skin, patients should report their most severe itching during the past week, rated according to a 0 to 10 scale, as itching is the most frequent cutaneous symptom of chronic GvHD. These are considered recommended measures. A semi-quantitative exploratory measure, “Your skin and/or joint tightening at its worst,” on a 0 to 10 scale has been added to capture severity of skin sclerosis. Informal cognitive testing suggested that including both “skin” and “joint” tightening in the question was not confusing for patients.
- For mouth, patients should report their mouth sensitivity (irritation resulting from normally tolerated spices, foods, liquids, or flavors), rated according to a 0 to 10 scale for peak severity during the past week.
- For genital tract, both female and male genital symptoms may be captured by the exploratory item rating “worst genital discomfort” on a scale from 0 to 10.
- For eyes, patients should report a “chief eye complaint” rated according to a 0 to 10 scale for peak severity during the past week. The complaint can change from visit to visit, but only 1 “chief eye complaint” is graded.

### **9.3. Response criteria**

- Numbering of weeks/timing of events

Week 1 is the week corresponding to the first infusion of ATO. Weeks are counted from this week onwards, unless stated to the contrary. Investigators should take care not to confuse weeks post-ATO with weeks post-transplantation.

➤ Response to the study regimens:

- Assessment of response (CR vs. PR): The main issue in chronic GvHD is the lack of consensus criteria for the assessment of the response. In 2015 an NIH sponsored meeting was held with a panel of experts on chronic GvHD. Their proposal for grading of chronic GvHD will be used in this protocol (see Appendix 1).
- The following definitions will be used:
- Complete remission (CR) is defined as complete disappearance of any sign of chronic GvHD
- Partial remission (PR) is defined as improvement of 1 or more point on a 4 to 7-point scale or an improvement of 2 or more points on a 10 to 12-points scale in at least 1 organ or site without progression in any other organ or site. For patients with BOS, an absolute improvement in %FEV1 of 10% predicted or more (eg, 50% to 60%) is considered a PR as long as the initial % FEV1 is < 70%. Normalization ( $\geq 80\%$ ) is considered a CR.
- Progressive disease (PD) is defined as at least one organ system has worsened by at least one stage without improvement of any other organ systems from baseline
- For skin, eye, esophagus, and upper and lower GI tract, a worsening of 1 point or more on the 0 to 3 scale is considered progression, except a change from 0 to 1, which is considered trivial progression since it often reflects mild, nonspecific, intermittent, self-limited symptoms and signs that do not warrant a change of therapy.
- For joint/fascia, a worsening of 1 point or more on the 0 to 3 scale is considered progression, even if from 0 to 1, because a change to score 1 was considered meaningful progression that would prompt a change in therapy. For joints assessed by the photographic range of motion, a worsening of 1 or more points for the 7-point scales and 1 or more points for the 4-point scale is considered progression.

- For mouth, a worsening of 2 or more points on the 1-point scale indicates progression.
- Worsening of liver GvHD is defined by an increase of 2 or more times the upper limit of normal for the assay for alanine transaminase, alkaline phosphatase, or total bilirubin.
- For patients with lung involvement, absolute worsening of FEV1 by 10% predicted or more (eg, 50% to 40%) is considered progression, as long as the final %FEV1 is < 65% (because initial %FEV1 must be < 75% to establish the diagnosis of lung involvement). If PFTs are not available, then worsening of the clinical lung score based on symptoms by 1 or more points should be scored as progression, except from score 0 to 1, which is considered trivial progression because of its lack of specificity for lung chronic GvHD.
- Mixed response is defined as CR or PR in at least one organ accompanied by progression in another organ
- Unchanged: outcome that does not meet criteria for CR, PR, PF or mixed response are considered unchanged
- Resistance is defined as lack of a CR/PR 2 weeks after the last ATO infusion, requirement for alternative therapy or death from GvHD before the last ATO infusion
- Failure is defined as death, recurrent or progressive malignancy or the initiation of new systemic treatment for chronic GvHD increased dosing of existing treatment will not be considered as failure

#### **9.4. Infections**

These will be classified, as far as is possible, by pathogenic agent, clinical syndrome, and localization according to the definitions of the Infectious Diseases Working Party of the EBMT, available on the website of the EBMT:

<https://www.ebmt.org/Contents/Research/TheWorkingParties/IDWP/Pages/Infectious-Diseases.aspx>

Date of onset, duration, treatment and outcome will also be noted, as well as prophylaxis prior to infective episode.

#### **9.5. Cause of death**

When determining the cause of death, investigators should classify deaths occurring from infection and from multiple organ failure in the presence of chronic GvHD, as being caused or related to GvHD.

## **10. Statistical considerations**

### **10.1. General considerations**

A statistical analysis plan which describes the statistical analyses planned for the study will be written and signed before database lock.

Data will be described using qualitative and quantitative data as follows:

- Qualitative data will be described in frequency and percentage and will be represented using histograms or diagrams of distribution
- Quantitative data will be described using the calculations of average, standard deviation, median, and extreme values

### **10.2. Analyses data set**

Every patient included in the study and who has received at least one infusion of ATO will be taken into account at time of data analysis.

Patients who do not receive any injection of ATO will not be analyzed and will be replaced to obtain 24 patients provided in the statistical analysis.

### **10.3. Statistical analyses**

A descriptive analysis will be conducted on the following parameters:

- Patients and transplant characteristics
- Primary and secondary endpoints

The toxicities rate will be calculated and will be given with their 95% confidence intervals.

The probabilities of survival will be estimated by the Kaplan-Meier method and by calculating the cumulative incidences for relapse/progression, and non-relapse mortality incidence.

## **10.4. Definition of Endpoints**

### **10.4.1. Efficacy success**

Efficacy success is defined as the response rate (CR+PR) at 6 months after the first ATO infusion, with no secondary systemic therapy (defined below) at any time. Death or dropout with lack of follow-up information after response of chronic GvHD but before the final analysis is expected to occur infrequently and will not be used to negate categorization as efficacy success for purposes of this study, since the treatment had been effective in controlling chronic GvHD. It is possible that systemic immunosuppressive treatment will be discontinued before resolution of all reversible manifestations of chronic GvHD in some patients. Topical therapy may be continued in this situation, at the discretion of the managing physician. Discontinuation of immunosuppressive medications for the purpose of inducing an anti-tumor response after the development of recurrent or secondary malignancy will not be categorized as efficacy success.

It is possible that initial treatment with ATO might improve the prospects of success after secondary systemic therapy. This endpoint will not be used, however, to avoid any confounding biases.

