### **10.4.2. Efficacy failure**

Efficacy failure is defined as early treatment failure is first checked at week 6 post ATO. Treatment failure will be defined as:

- Required initiation of a new systemic treatment for chronic GvHD before week 6
- Recurrent or progressive malignancy before week 6
- Death before week 6

Failure-free survival (FFS), is defined as death, recurrent or progressive malignancy, or the initiation of a new systemic treatment for chronic GvHD (defined below).

From the perspective of the patient, secondary therapy and death have very different significance with respect to efficacy, since the need for secondary therapy does not inevitably lead to death. From the perspective of the clinical trial, however, both events indicate that the study-drug did not have the desired efficacy.

Discontinuation of treatment with study-drug because of toxicity will not be categorized as efficacy failure in and of itself, since it is possible that a short period of treatment with the study-drug could have long lasting benefit ultimately resulting in efficacy success. After a toxic study-drug outcome, patients will be followed for any subsequent initiation of secondary systemic treatment development of recurrent malignancy, death from causes other than recurrent malignancy, or dropout with lack of follow-up information. Any of these events occurring during primary treatment for chronic GvHD will be categorized as efficacy failure.

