### **10.7. Calculation of the number of patients**

Based on results from the literature, the hypothesis for the primary endpoint is an improvement in response rate (CR and PR) at 6 months after the diagnosis of chronic GvHD and start of ATO from 60% to 85%. Using a one-step A'Hern procedure (A'Hern RP, 2001) (and anticipating a dropout rate around 10%), 24 (21+3) patients are needed. If the number of successful cases is 17 or more among the 21 patients, the hypothesis that the CR rate at 6 months is less than 60% is rejected with a target error rate of 0.05 (alpha probability). The beta probability in this case is 0.2.

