12.4.3.2 Handling of Dropouts or Missing Data

Every effort will be made to keep the number of missing values for all parameters to a minimum. The number of missing values will be reported together with summary statistics for each variable.

Missing data on overall survival is assumed to be null as patient care after transplantation is very close. Any patient prematurely withdrawn or ending the study without the event of interest (progression, death) will be censored at his/her last information date.

Concerning the main endpoint (response at M6), the missing assessments will be fully discussed during the data review. The most plausible outcome (the clinically more relevant) will be used for the main analysis. Other methods of imputation (for example, worst

outcome: missing data=failure) could be used for sensitivity purpose, according to the final number of missing assessments.

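### The plan has no single rule for a responder who dies or drops out before month 6: Protocol 10.4.1 can keep the patient as a success, other sections point to failure, and the SAP gives two answers

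*Protocol*

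**What the plan says.** Protocol 10.4.1 defines efficacy success as complete or partial response at 6 months after the first infusion, without secondary systemic therapy. It then deals with patients who die or are lost after a response. Such an event, at any time up to the final analysis, "will not be used to negate categorization as efficacy success for purposes of this study". The section expects this to be infrequent and gives as its reason that treatment had controlled the disease.

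Other protocol sections classify such events differently:

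- The response definitions in the Synopsis, 7.3.2.1 and 9.3 list death as failure, with no time limit.
- Section 10.4.2 lists death before week 6 as treatment failure. It also says in general terms that death, like secondary therapy, shows that the drug did not achieve the desired effect.
- For patients followed after a toxic outcome, 10.4.2 lists secondary therapy, recurrent malignancy, death from other causes and dropout, and concludes: "Any of these events occurring during primary treatment for chronic GvHD will be categorized as efficacy failure".

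The SAP restates the endpoint in 8.2.1 without the 10.4.1 exemption. The derivation in 11.4.1.1 gives a yes only if the principal investigator judged the patient a responder at month 6, and a no in every other case. Section 12.4.3.2 sends missing month-6 assessments to discussion at data review: "The most plausible outcome (the clinically more relevant) will be used for the main analysis". Counting missing as failure is named only as a possible sensitivity analysis.

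**The concern.** Response is assessed at weeks 6 and 14 before it is assessed at month 6 (Protocol 8.1 and 9.2). A patient can therefore have a documented response and be lost before the time point that defines the endpoint. The wording of 10.4.1 lets such a patient count as a success without a month-6 assessment, and that exemption can only raise the rate.

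The SAP does not clearly close this gap. Its derivation gives one answer and its missing-data rule leaves another open. The open one is settled patient by patient, at a data review, in a single-arm trial without blinding. With 21 to 24 patients and a single cut-off, one such decision can change the trial's conclusion.

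**Working it through.** **1. The design as planned.** Inputs from Protocol 10.7: null rate 60%, target 85%, alpha 0.05, beta 0.2, dropout about 10%. The rule is: "If the number of successful cases is 17 or more among the 21 patients", the null is rejected.

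- P(X ≥ 17 | n = 21, p) = Σ C(21,k) p^k (1−p)^(21−k), for k = 17 to 21.
- At p = 0.60 this is 0.037. At p = 0.85 it is 0.8025.
- In a search upwards from n = 15, 21 is the first size with exact alpha ≤ 0.05 and power ≥ 0.80.
- 21/0.90 = 23.3, rounded up to 24.

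The plan's figures reproduce.

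**2. One patient under each rule.** Take a week-6 responder who dies, or drops out, at month 4.

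| Place | Death | Dropout |
|---|---|---|
| Protocol 10.4.1 | can stay a success | can stay a success |
| Protocol Synopsis, 7.3.2.1, 9.3 | failure | not listed |
| Protocol 10.4.2, general statement | lack of efficacy | not addressed |
| Protocol 10.4.2, after a toxic outcome, during primary treatment | failure (unless from recurrent malignancy, itself listed as failure) | failure |
| SAP 11.4.1.1 | non-response | non-response |
| SAP 12.4.3.2, if handled as a missing assessment | open | open |

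**3. What one patient is worth.** 1/24 = 4.2 points and 1/21 = 4.8 points. 17/21 = 81.0% meets the rule. Reclassifying one, two or three patients gives 16/21 = 76.2%, 15/21 = 71.4% or 14/21 = 66.7%, and none of these meets it.

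SAP 11.4.1.1 uses a 95% Clopper-Pearson lower bound instead. I read the criterion as a bound above 60%, although the text there says lower. On that reading 17/21 (bound 58.1%) fails and 18/21 (bound 63.7%) passes. One patient still separates the two conclusions.

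**4. Illustration of the effect on error.** The documents give no rate for responders lost before month 6, so these are assumptions. Suppose 10% are lost before month 6 and 60% to 80% of them had responded. Keeping those patients as successes adds 0.10 × 0.60 = 6 points to 0.10 × 0.80 = 8 points. A true 60% is then counted as 66% to 68%.

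| Counted rate | P(≥ 17/21) | P(≥ 18/21) |
|---|---|---|
| 60% | 0.037 | 0.011 |
| 66% | 0.109 | 0.041 |
| 68% | 0.149 | 0.060 |

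Over a wider range (5% to 12.5% lost, 50% to 100% of them prior responders) the counted rate runs from 62.5% to 72.5%, and P(≥ 17/21) from 0.060 to 0.275.

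**5. Cost of counting loss as non-response.** If 10% are lost independently of response, 85% becomes 0.85 × 0.90 = 76.5%. P(≥ 17/21) is then 0.43, against 0.80 planned. With 24 analysed and the exact cut-off of 19 (alpha 0.040), it is 0.49. Under the null, 60% becomes 54%, and P(≥ 17/21) is 0.010.

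**The case against.** **The SAP already decides the case.** Section 8.2.1 drops the exemption, and 11.4.1.1 scores the month-4 death as non-response. This largely stands: a reader might infer that such a patient will be counted as a success, but the written derivation says otherwise. What remains open is 12.4.3.2, which reaches the main analysis and is not reconciled with 11.4.1.1.

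**10.4.1 may mean only month-6 responders lost later.** Follow-up runs to 12 months, so this is a possible reading. The text does not say it, and the period up to the final analysis includes the months before month 6.

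**10.4.1 and 10.4.2 do not flatly contradict each other.** A reader might infer that 10.4.2 makes every death or dropout a failure. It does not. The sentence on dropout follows the discussion of toxic outcomes and is limited to primary treatment. The other listed failures fall before week 6, when response is first formally assessed. The direct clash is therefore limited to patients with a toxic outcome. The general statement on death and the untimed failure definitions extend it to deaths, but not to dropouts.

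**The bias need not run one way.** This is correct for the SAP: a most plausible outcome can be failure as well as success. Only the 10.4.1 exemption is one-directional.

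**The error figures rest on assumptions.** This also stands. The 10% is the allowance that raised 21 to 24, its split by prior response is not given, and 10.4.1 expects few such cases. The SAP analysis set also requires a week-6 evaluation (11.1), so the earliest losses never reach this rule. At 18/21 the inflated error is close to the nominal 0.05.

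**Conclusion.** The concern holds as a missing and inconsistent rule for the primary endpoint. Protocol 10.4.1 permits a responder lost before month 6 to remain a success. This conflicts with the untimed failure definitions for deaths, with the general statement in 10.4.2, and with the 10.4.2 rule for patients followed after a toxic outcome. SAP 11.4.1.1 and 12.4.3.2 give different answers for the same patient.

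The firm part of the size is 4.2 to 4.8 points per patient, with one patient enough to cross the threshold. The rise from 0.037 to 0.109–0.149 (to 0.041–0.060 at 18/21) depends on the assumed losses and on the cut-off. It illustrates sensitivity and is not the trial's expected error rate. The documents do not support the inference that the main analysis will be inflated: a strict application of 11.4.1.1 would prevent it.

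**What to change.** - In Protocol 10.4.1, limit the exemption to death or dropout after the month-6 assessment.
- In the protocol and SAP 12.4.3.2, state that death, dropout or a missing assessment before month 6 is non-response in the main analysis. This agrees with the derivation in SAP 11.4.1.1. Align 10.4.2 and the failure definitions with it.
- Keep the most plausible outcome as a sensitivity analysis only.

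This is a change of wording and needs no new data, but it has a cost that should be disclosed. The estimate becomes less favourable, and a 10% loss independent of response would cut power at 17/21 from 0.80 to about 0.43 (0.49 at 19/24). The sponsor should say whether the 60% and 85% rates already count such losses as failures, since the documents do not, and should revisit the target rate or sample size if they do not.
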